## 4.6 Validity Review

The results of the validity review meeting will be documented in the Validity Review Report and may comprise decisions and details relevant for statistical evaluation. Any changes to the statistical analysis prompted by the results of the validity review meeting will be documented in an amendment and, if applicable, in a supplement to this SAP.

## 5. Analysis Sets

## 5.1 Assignment of analysis sets

#### Part 1 (CHICO)

#### Full analysis set (FAS)

The efficacy analyses will be done using the full analysis set (FAS), which is the set of randomized subjects who received at least one dose of study drug.

Analyses of safety and background data will be performed on the FAS.

#### Per protocol set (PPS)

The primary analysis will also be done using the per-protocol set, which is comprised of randomized subjects treated with study drug who have no major protocol deviations. Major protocol deviations defined in this study will include:

- Subjects who have both conventional serology results missing at the 12-month time point
- Subjects who do not meet in-/exclusion criteria but entered treatment phase
- Subjects who take less than 80% or more than 120% of total assigned doses of study drug
- Subjects whose treatment codes are unblinded during the study
- Subjects who have taken prohibited medicine during the study

## Part 2 (CHICO SECURE)

#### Full analysis set (FAS)

The efficacy analyses will be done using the full analysis set (FAS), as defined in part 1. Subjects will be analyzed as randomized in part 1 (CHICO) of the study.

Analyses of safety and background data will be performed on the FAS. For safety analyses, subjects will be analyzed as treated in part 1 of the study.

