9.2.4.1 Eligibility procedures (FU Visit 1)

After the consent/assent has been obtained, eligibility assessments will be performed at the first visit. The first visit should be performed as soon as possible after availability of regulatory and ethics committee approval for all subjects who have already completed part 1 of the study for 1 year \pm 6 weeks or longer. Subjects who completed part 1 of the study 10.5 months or less prior to the start of the LTFU will be informed about part 2 of the study and will have their eligibility assessments according to the visit schedule provided that consents/assents have been obtained.

The subject's update on medical history and concomitant medication will be recorded.

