10.2 Analysis sets

Part 1 (CHICO)

The primary efficacy analysis will be done using the full analysis set (FAS), which is the set of subjects who received at least one dose of study drug. Analyses will also be done using the per-protocol set, which is comprised of subjects treated with study drug who have no major protocol deviations. Complete specifications will be provided in the SAP.

Analyses of safety and background data will be performed on the FAS.

Part 2 (CHICO SECURE)

The primary efficacy analysis will be done using the full analysis set (FAS) as defined in part 1. Subjects will be analyzed as randomized in part 1 (CHICO) of the study. Complete specifications will be provided in the SAP.

¹⁷⁹ Modified as per amendment 2

¹⁸⁰ Text modified/added for clarity (Amendment 1)

	Integrated Clinical Study Protocol BAY A2502/16027	
03 NOV 2020	Version 11.0	Page: 78 of 259

Analyses of safety and background data will be performed on the FAS. For safety analyses, subjects will be analyzed as treated in part 1 of the study.

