## **Adverse Events**

All adverse events occurring during the study (i.e., from signing of informed consent until last visit) will be reported. The MedDRA coding system will be used to code the adverse events.

An overview of frequencies of subjects who died, experienced any adverse event, experienced any drug-related adverse event, experienced a serious adverse event (SAE), experienced a drug-related serious adverse event, or discontinued due to an adverse event will be summarized by treatment regimen.

Adverse events will be considered treatment emergent, if they first occurred or worsened at or after first application of study medication during the course of the study up to and including 7 days after last application of study medication.

Incidence of treatment emergent AEs (TEAEs), drug-related TEAEs, serious TEAEs, drugrelated serious TEAEs, as well as TEAEs leading to discontinuation will be summarized by primary system organ class and high level term by treatment regimen.

The definitions of incidence are as follows:

- Incidence of all events: # of subjects reporting the event with a start date during or after treatment/# of subjects valid for safety.
- Incidence of drug-related events: # of subjects reporting a drug-related event with a start date during or after treatment/# of subjects valid for safety.
- Incidence of events by maximum intensity: # of subjects reporting the event at the indicated intensity with a start date during or after treatment/# of subjects valid for safety.

Adverse events leading to death, premature discontinuation and serious adverse events will be listed. In this study, all AEs of urticarial, weight loss of > 20%, severe rash, and severe polyneuropathy will be considered AEs of special safety interest. Adverse events of special safety interest will be summarized by treatment regimen.

AEs occurring between the time of consent and the first dose of study drug will be summarized separately.

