## Part 2 (CHICO SECURE)

According to Sosa-Estani [7, 7], the 48 months post treatment cure rate for benznidazole is about 5% as confirmed by two types of assay. For the primary objective, assuming a drop-out rate of 15%, the expected number of patients to be observed at the end of Part 2 (i.e. 48 months post treatment) in the 60-day regimen would be 170 out of the 200 patients in Part 1. Using the assumptions of 170 nifurtimox 60-day regimen patients in Part 2, a 5% cure rate, and that seronegative conversion events follow Poisson distribution, the estimated incidence rate is calculated to be 1.32% and the 95% CI of the incidence rate is (0.61%, 1.51%).

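### Part 2 safety is analysed on the Part 1 full analysis set, so children who never enter Part 2 stay in the denominator of any crude Part 2 adverse event percentage and pull it down.

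*SAP*

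**What the plan says.** **Population.** For Part 2, SAP 5.1 says: "The efficacy analyses will be done using the full analysis set (FAS), as defined in part 1". It then puts safety on the same set: "Analyses of safety and background data will be performed on the FAS. For safety analyses, subjects will be analyzed as treated" in Part 1. The set is defined under Part 1 in the same section: "which is the set of randomized subjects who received at least one dose of study drug". Protocol 10.2 agrees for Part 2: "The primary efficacy analysis will be done using the full analysis set (FAS) as defined in part 1", with safety and background data also on the FAS and children counted as treated in Part 1. Neither document defines a set restricted to children who entered Part 2.

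**Entry.** Part 2 is a separate step. Protocol 9.2.4.1 says: "After the consent/assent has been obtained, eligibility assessments will be performed at the first visit". Protocol 6.2 lists six exclusion criteria for Part 2. Among them are housing without vector control and an investigator's view that the child is unlikely to complete follow-up.

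**Collection.** Protocol 9.2.4.2, 9.2.4.3 and Table 9-2 place Part 2 adverse event collection at the annual site visits and the interim phone contacts.

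**Summary.** Protocol 10.3.2.2 plans descriptive statistics and/or frequency tables by treatment group for Part 2 safety. SAP 4.1 plans counts and percentages for categorical variables. SAP 6.3 writes an incidence formula only under Part 1: "of subjects reporting the event with a start date during or after treatment/# of subjects valid for safety". It does not define who is valid for safety.

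**The concern.** Counting children as treated in Part 1 settles which regimen they belong to. It does not settle whether they were followed in Part 2. A child who declines consent, is excluded or cannot be re-contacted has no scheduled Part 2 adverse event collection. In practice that child adds 0 to the numerator and 1 to the denominator, and so is treated as having been observed without an event.

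Some non-entry is foreseeable. Protocol 5.2 expects first visits from families whose Part 1 participation ended a year or more earlier, some of them beyond the visit window.

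Part 2 safety is descriptive only, so these percentages are themselves the adverse event result of the long-term follow-up. The efficacy analysis avoids the problem because its denominator is person-years (SAP 4.3 and 6.2.2.1), to which a child contributes only the time observed. Nothing equivalent is planned for adverse events.

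**Working it through.** **Inputs**

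- FAS, 60-day arm: 200 (SAP 6.5 and Protocol 10.4, Part 2).
- Loss by month 48: "assuming a drop-out rate of 15" per cent (SAP 6.5, Part 2).
- Expected at the end of Part 2, 60-day arm: 170 (same place).
- Total randomised: about 300 (SAP 3.1).
- Fraction of the FAS that never enters Part 2, *q*: not given in either document, so any value is an assumption.

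**Step 1: reproduce the plan's figure.** 200 × (1 − 0.15) = 170. It reproduces exactly.

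**Step 2: the dilution.** Let *F* be the FAS count, *m* the number who enter Part 2 and *e* the number with an event. The printed percentage is *e*/*F* and the percentage among entrants is *e*/*m*. Hence printed = (percentage among entrants) × *m*/*F*, with *m*/*F* = 1 − *q*. Any non-zero percentage is understated as soon as one FAS child does not enter.

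**Step 3: the size for assumed values of *q***

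| Non-entry *q* | Entrants of 200 | Printed ÷ among entrants | Among entrants ÷ printed | 10% among entrants prints as |
|---|---|---|---|---|
| 5% | 190 | 0.95 | 1.05 | 9.5% |
| 10% | 180 | 0.90 | 1.11 | 9.0% |
| 15% | 170 | 0.85 | 1.18 | 8.5% |

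**Step 4: where the plan's 15% fits.** The 170 are those still observed at month 48. The 15% therefore mixes children who never entered with children who entered and left later. Only the first group causes this dilution. Under the plan's own assumption *q* is at most 15%, and the factor of 0.85 is reached only if every loss is a non-entry. In that worst case, 10 children with an event give 10/200 = 5.0% printed against 10/170 = 5.9% of those followed. For both arms together the denominators would be 300 and 300 × 0.85 = 255.

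**Step 5: between regimens.** If non-entry were 5% in one arm and 15% in the other (illustration only), the same 10% among entrants would print as 9.5% and 8.5%. That gap comes from entry alone.

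**Step 6: is it corrected elsewhere?** SAP 6.3 for Part 2 gives no other denominator. SAP 6.1.1 summarises disposition on the FAS by study phase and regimen, but does not name entry to Part 2. A reader may therefore be unable to undo the dilution from the planned tables.

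**The case against.** **The crude Part 2 percentage is inferred.** The only written incidence formula belongs to Part 1, its denominator is an undefined term, and treatment-emergent events end 7 days after the last dose. This is fair: the Part 2 denominator follows from the population rule in SAP 5.1, not from a formula. But that rule is explicit, and frequency tables and percentages are planned for Part 2 safety. An analyst who follows the text would divide by the FAS.

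**An entrants-only set is selected after treatment.** The Part 2 criteria remove children with certain manifestations of the disease or an expected failure to complete, while the FAS keeps randomised membership. This stands. It is a reason to report non-entry by regimen next to the percentages. It does not justify counting unfollowed children as event-free.

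**Disposition already shows losses.** Only partly, as Part 2 entry is not a named category.

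**Stronger readings.** A reader might infer that every Part 2 figure is printed at 85% of its true value, or that entry could be far lower still. The documents support neither: 15% is total loss by month 48, and no entry rate is stated. A reader might also extend the point to all Part 2 safety output. By-visit ECG and vital-sign summaries rest on values observed at each visit and are not diluted in this way. Nor are FAS background tables wrong in themselves, since they describe the population of the primary Part 2 incidence rate. Finally, nothing in the documents suggests that entry differs by regimen, so distortion between arms is only a possibility.

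**Conclusion.** The point holds for crude Part 2 adverse event percentages and any other crude Part 2 safety percentage taken over the FAS. The direction is certain once one FAS child does not enter, given that non-entrants have no Part 2 collection. The size is unknown because non-entry is not stated. Under the plan's loss assumption the printed figure falls at most to 85% of the figure among entrants, a gap of 0.9 percentage points in the example of 10 events. At 5% or 10% non-entry it is 95% or 90%. Efficacy is untouched and no hypothesis test changes. This is a correction that should be made, of modest expected size.

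**What to change.** In SAP 5.1 and Protocol 10.2:

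- Define a Part 2 safety set: FAS children with Part 2 consent and at least one Part 2 visit or contact, analysed as treated in Part 1.
- Use it as the denominator for Part 2 adverse event percentages and other crude Part 2 safety percentages.
- Report by regimen how many FAS children did not enter Part 2.
- Keep the FAS for the Part 2 incidence rate and its baseline tables, and add one baseline table for Part 2 entrants.

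The cost is one population flag, one extra table and a few lines of wording, with no new data. The percentages become slightly less favourable. Entrants remain a group selected after treatment, which the non-entry counts by regimen make visible but do not remove.

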## 6. Statistical Methodology

## 6.1 **Population characteristics**

## 6.1.1 Disposition

Disposition will be summarized descriptively for the study phases of screening, treatment, and follow-up for FAS. The number of subjects discontinuing the screening phase together with the primary reason for discontinuation will be presented overall. The number of subjects discontinuation will be presented overall and by treatment regimen. In addition, the number of subjects with major/important protocol deviations will be presented overall and by treatment regimen. Subjects discontinuing the study due to COVID-19 and any protocol deviation caused by COVID-19 will be summarized accordingly.

## 6.1.2 Demographic and Other Baseline Characteristics

Demographics (sex, ethnicity, race, age at randomization, weight, height/length) and baseline characteristics (i.e., ELISA, IHA and qPCR test results, Chagas' disease signs and symptoms) will be summarized overall and by treatment regimen. The same summary will also be performed for each age stratum.

## 6.1.3 Medical History

For data coding, Medical Dictionary for Regulatory Activities (MedDRA) [version 18.0 or most recent version] will be used for medical history. Medical history (i.e., previous diagnoses, diseases or surgeries) not pertaining to the study indication, start before signing of the informed consent and considered relevant to the study will be presented for each MedDRA primary system organ class and high level term by treatment regimen and overall using frequency counts.

Concomitant medications will be tabulated by treatment regimen using ATC codes (WHO-DD); frequencies of subjects having received each drug category will be provided.

## 6.1.4 Extent of Exposure and Compliance

## Part 1 (CHICO)

BAY No. A2502/IMPACT No. 16027 Page: 16 of 30

All summaries related to intake of study medication will be by treatment regimen based on FAS.

The treatment duration will be summarized descriptively overall and for each age stratum. It will be calculated as follows:

Treatment duration = (drug stop date - drug start date + 1 day).

If the end date of the first drug distribution and the start date of the second drug distribution are the same, the calculation is:

Treatment duration = (drug stop date- drug start date for the  $1^{st}$  distribution) + (drug stop date- drug start date for the  $2^{nd}$  distribution + 1)

The number of tablets and corresponding extent of exposure (by dose) will be summarized descriptively. Compliance is defined as 100 \* number of tablets taken / number of tablets per protocol. The compliance will be summarized descriptively by treatment regimen and overall. In addition, compliance will be categorized into three groups (<80%, 80-120%, >120%) and summarized by treatment regimen and overall.

## Part 2 (CHICO SECURE)

Not applicable.

## 6.2 Efficacy

## 6.2.1 Part 1 (CHICO)

## 6.2.1.1 Primary efficacy variable and analysis

The primary efficacy variable will be sero-reduction (defined as  $a \ge 20\%$  reduction in optical density [OD]) or sero-conversion (defined as negative Immunoglobulin G [IgG] concentration) in the 60-day regimen group at 12 months post-treatment using two conventional ELISA serology tests. This sero-reduction (in subjects  $\ge 8$  months to < 18 years of age at randomization) or sero-conversion (in all subjects) is considered cure, and the primary variable is binary (cure, no cure). In the event of discordancy between the two conventional ELISA test results, the following will be considered:

• For sero-reduction, the average percentage of OD reductions for the two conventional ELISA tests will be used (e.g., Test #1 = 15% and Test #2 = 25%; average = 20% and, hence, cure).

BAY No. A2502/IMPACT No. 16027

Page:

- For sero-conversion, only when both test results are negative that the subject is considered as negative (i.e., cure).
- If one of the test results is missing, the subject is considered as "no cure".

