Since 1991, the estimated global prevalence of *T. cruzi* infection has decreased from 18 million to 8 million due to intensive vector control and blood bank screening. The PAHO estimates that approximately 60,000 new *T. cruzi* infections occur each year [1]. As other transmission routes have diminished, the proportion of infections attributable to congenital infection has increased. An estimated 26% of incident infections now occur through mother-to-child transmission. Mortality among infected infants is significantly higher than in uninfected infants, ranging from less than 5% to 20% in published studies [7][8]. However, even severe congenital Chagas' disease may not be recognized because signs are often nonspecific, or because the diagnosis is not considered. Children younger than 2 years of age appear to be at higher risk of severe manifestations than older individuals. Severe acute Chagas' disease carries a substantial risk of mortality [8].

In *T. cruzi* infection, treatment with nifurtimox reduces the severity of symptoms, and shortens the clinical course and duration of detectable parasitemia. Parasitological cure is reported in 60% to 85% of patients treated in the early phase. Furthermore, published evidence suggests that if the duration of infection is less than 1 year, the percentage of patients cured (i.e., elimination of parasites) approaches 100% [5][6].

Nifurtimox is well tolerated in children, but its pharmacology in the pediatric population is still not well defined. The currently available marketed product was developed for adults, and there is a significant need for a pediatric formulation particularly for infants and newborns to support weight-adjusted dosing.³³ The safety profile of the drug is relatively well-

³² Text modified for clarity (Amendment 1)

³³ Text modified for clarity, and per changes as a result of Amendment 1

	Integrated Clinical Study Proto	ocol
	BAY A2502 / 16027	
03 NOV 2020	Version 11.0	Page: 24 of 259

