6.3.1 Withdrawal

Withdrawal criteria

Subjects *must* be withdrawn from the study if any of the following occurs:

• At their own request or at the request of their parents' or legally acceptable representative. At any time during the study and without giving reasons, a subject may

	Integrated Clinical Study Protocol	
	BAY A2502 / 16027	
03 NOV 2020	Version 11.0	Page: 40 of 259

decline to participate further. The subject will not suffer any disadvantage as a result of this decision.

- Pregnancy. If any urine pregnancy test is positive, a serum pregnancy test must be performed to confirm the result. See Section 9.6.2.⁹⁴ (not applicable to part 2)
- Subjects, with positive parasitology test at the 30-day visit for whom (1) it has been determined that the drug was administered correctly and (2) the daily dosage given was correct, must be discontinued from the study and treated with an alternative trypanocidal medication, selected by the investigator.⁹⁵ (not applicable to part 2)

Subjects *may* be withdrawn from the study if any of the following occurs:

- If, in the investigator's opinion, continuation of the study would be harmful to the subject's well-being
- At the specific request of the sponsor and in liaison with the investigator (e.g., obvious non-compliance, safety concerns)
- For the following situations that are regarded by the investigator to be related to the use of study drug (nifurtimox) (not applicable to part 2):
 - Severe nervous system disorders such as seizure, vertigo/dizziness, polyneuropathy, or peripheral neuropathy
 - Severe gastrointestinal disorders, severe decreased appetite
 - Significant loss of body weight in the judgment of the investigator
 - Severe hepatic impairment
 - Severe renal impairment
 - Psychic disorders such as disorientation, psychotic behavior
 - Development of malignant disease
 - Hematological abnormalities such as severe leukopenia

Depending on the time point of withdrawal, a withdrawn subject is referred to as either "screening failure" or "dropout" as specified below:

Screening failure

A subject who, for any reason (e.g., failure to satisfy the selection criteria), terminates the study before the time point used for the definition of "dropout" (see below) is regarded as a "screening failure."

Re-starting the defined set of screening procedures to enable the "screening failure" subject's participation at a later time point is allowed only in the following situations (not applicable to part 2):

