9.4.3 Concentration tests for *T. cruzi*

Concentration tests for *T. cruzi* will be performed on all subjects < 8 months of age at randomization at the screening visit, and at Visits 3, 6, 8 and 9.

Details describing the collection, processing, storage and shipment of blood samples, and the concentration test protocol, will be described in a separate manual. Concentration tests for *T. cruzi* will be performed by a local laboratory according to the standard of care for each country.¹⁵⁶

Concentration test for *T. cruzi* is not applicable for subjects in part 2 of the study. However, concentration test for *T. cruzi* may be performed in children born of female study subjects to detect congenital infection (see Section 9.6.2).

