## 4.2 Handling of Dropouts

A subject who discontinues study participation prematurely for any reason is defined as a "dropout" if the subject has already been randomized, assigned to treatment, and administered at least one dose of study drug.

A subject who, for any reason (e.g., failure to satisfy the selection criteria), terminates the study before the time point used for the definition of "dropout" is regarded as a "screening failure".

Depending on the time point of withdrawal, a withdrawn subject is referred to as either "screening failure" or "dropout". A subject who is withdrawn from the study will not be replaced.

Subjects who discontinue prematurely from study drug administration will continue to return to the investigational site for study assessments at Visits 3, 6, and 8 (EOT), and undergo telephone assessments as described for Visits 4, 5, and 7. If subjects are unable/unwilling to do so, they must return to the investigational site 30 ( $\pm$ 3) days after the last dose of study drug for EOT (Visit 8) assessments, and undergo telephone assessments as described for Visits 4, 5, and 7. If the subject is unable/unwilling to return to the clinic for the EOT Visit (Visit 8), then a telephone assessment as described for Visits 4, 5, and 7 may be performed in lieu of Visit 8 assessments.

Premature discontinuations from study drug will be summarized by treatment regimen, both for any type of discontinuation, and for each specific reason for discontinuation.

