## 4.3 Handling of Missing Data

#### Part 1 (CHICO)

No imputations will be made for missing values occurring in the safety and background variables. Background variables include demographics (sex, age), height/length, weight, medical/surgical history, and medication history.

All efforts will be taken to collect all data. However, despite best efforts, it may be inevitable that missing data are reported. In the primary efficacy analysis done on the full analysis set (FAS), subjects who have missing conventional serology results at the 12 month time point will be treated as failures (i.e. no cure).

For the secondary analysis using the per-protocol set (PPS), all subjects who do not have both conventional serology determinations to assess the 12-month time point will be excluded from the analysis.

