#### Sensitivity analyses of the primary efficacy variable

The following sensitivity analyses for the primary efficacy variable will be performed:

- Missing values due to the following reasons treated as treatment failures and other missing values excluded from analysis:
  - 1. the reason for discontinuation is known or suspected to be treatment ineffectiveness or an AE,
  - 2. a subject has not had a negative serology at any visit and has no serology determination for the primary analysis visit,
  - 3. an indeterminate or incorrectly performed serology determination occurs at the primary analysis visit (e.g. missing values due to lab procedure, not enough sample materials to perform the test, performance error, etc.).
- Observed data only
- Analysis on PPS

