## 6.2.2 Part 2 (CHICO SECURE)

## 6.2.2.1 Primary efficacy variable and analysis

## Primary efficacy variable

The primary efficacy variable will be the incidence rate of seronegative conversion measured and confirmed by two types of assay (recombinant ELISA and IHA) in subjects who were randomized and received at least one dose of the 60-day nifurtimox treatment regimen. Both test results should be negative for the subject to be considered as seroconverted. Incidence rate is the number of new cases of seronegative conversion over the study period (i.e. 4 years after end of nifurtimox treatment) divided by the person-time at risk.

Subjects used antitrypanosomal drugs during the study before they were seroconverted will not be considered as sero-convertion, but their time of observation till when they took antitrypanosomal drugs will be factored into the person time calculation.

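### Part 1 cure has no rule for non-study antitrypanosomal drugs taken before the 12-month ELISAs, although Part 2 has one

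*SAP*

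**What the plan says.** **Part 1.** SAP 6.2.1.1 counts sero-reduction (children aged 8 months or more at randomization) "or sero-conversion (in all subjects) is considered cure, and the primary variable is binary (cure, no cure". Its handling rules cover discordant and missing ELISA results only. Under SAP 4.3, "subjects who have missing conventional serology results at the 12 month time point will be treated as failures". The first sensitivity analysis also acts only on gaps in the data: "Missing values due to the following reasons treated as treatment failures and other missing values excluded from analysis". The other two use observed data and the per-protocol set.

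**Part 2.** SAP 6.2.2.1 has an explicit rule: "Subjects used antitrypanosomal drugs during the study before they were seroconverted will not be considered as sero-convertion". Person-time is kept up to the point when the drug was taken. The study period there is four years from the end of nifurtimox treatment. SAP section 1 places the first of those years in Part 1. Protocol 6.2 also says that subjects needing such treatment after nifurtimox are to be analyzed separately, but only in the justification of the Part 2 criteria.

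**Retreatment in Part 1.** Protocol 6.3.1 gives one provision. A correctly dosed child with positive parasitology at Day 30 "must be discontinued from the study and treated with an alternative trypanocidal medication". Protocol 9.4.3 schedules concentration tests for infants under 8 months "at randomization at the screening visit, and at Visits 3, 6, 8 and 9", without saying what follows a positive result at Visit 8 or 9.

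**The concern.** A negative or reduced ELISA reached after another antitrypanosomal drug is not evidence for nifurtimox. The Part 1 definition is mechanical, so silence amounts to credit: if the child has both 12-month results, they are scored as they stand.

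The two parts can then disagree on one child at one visit. Take a 60-day infant retreated after Day 90 who is negative on both ELISAs and on IHA at Visit 11 (Protocol Table 9–1 schedules IHA there if specimens suffice). SAP 6.2.1.1 makes this child a cure. SAP 6.2.2.1, as worded, does not count the child as converted.

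Against a fixed external benchmark, unadjusted scoring can only raise the 60-day rate. For the exploratory benznidazole comparison in SAP 6.2.1.3, the credited drug could be benznidazole itself.

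**Working it through.** **Inputs.** 200 and 100 children and a 55% cure rate (Protocol 10.4); continuity-corrected interval (SAP 6.2.1.1); thresholds of 16% (SAP 6.2.1.1) and 45% (SAP 6.2.1.3). SAP 6.5 still carries 260 and 130; the effect is shown at step 3.

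**1. The plan's own figure.** Lower limit = p − 1.96·√(p(1−p)/n) − 1/(2n). With n = 200:
- 43/200: 0.2150 − 0.0569 − 0.0025 = 15.56%
- 44/200: 0.2200 − 0.0574 − 0.0025 = 16.01%

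At least 44 cures are needed. The exact binomial power at a true rate of 55% is above 99.99%, so the stated 99% reproduces.

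**2. The 16% goal.** The expected count is 0.55 × 200 = 110. Falling to 43 takes 110 − 43 = 67 reclassifications. Even if 40% of expected cures were reclassified (true rate 33%), power would be 99.98%.

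**3. The 45% criterion.**

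| Cures | Lower limit | Reclassifications that overturn it |
|---|---|---|
| 100/200 | 42.82% | already fails |
| 104/200 | 44.83% | already fails |
| 105/200 | 45.33% | 105 − 104 = 1 |
| 110/200 | 47.86% | 110 − 104 = 6 |
| 120/200 | 52.96% | 120 − 104 = 16 |
| 130/200 | 58.14% | 130 − 104 = 26 |

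With n = 260 the minimum is 134. At 55% (143 cures) it takes 143 − 133 = 10 reclassifications. At a true rate of 55% and n = 200, the chance of meeting the criterion is 78.3%. It falls to 68.1% if 2% of expected cures are reclassified and to 50.0% at 5% (5.5 cases).

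**4. How many children could be affected.** The documents give no retreatment rate. Infants are the group with scheduled concentration tests after Day 30. Their number in the 60-day arm is 2 strata × stratum size × 2/3. Only 38 per stratum comes from the plan, where it is targeted but not required; 20 and 10 are my assumptions.
- 38 per stratum: 50.7 infants; six cases = 12%
- 20 per stratum: 26.7 infants; six cases = 23%
- 10 per stratum: 13.3 infants; six cases = 45%

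Assume that 2% to 10% of 60-day infants are retreated and later negative. The range runs from 0.02 × 13.3 = 0.3 cases to 0.10 × 50.7 = 5.1 cases, or 0.1 to 2.5 points on a denominator of 200.

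**5. 60 versus 30 days.** One case moves the difference by 1/200 = 0.5 point or 1/100 = 1.0 point, depending on the arm. Equal rates in both arms cancel. In an assumed extreme, 10% of 30-day infants only (76/3 = 25.3 infants, 2.5 cases) moves it by 2.5 points. The half-width at 55% in both arms is 1.96·√(0.2475/200 + 0.2475/100) + ½(1/200 + 1/100) = 12.7 points.

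**The case against.** The strongest reply is that Part 1 did not need such a rule. Its only stated retreatment provision ends in discontinuation, so 12-month serology is normally missing and SAP 4.3 scores the child as a failure. Protocol 8.2 places the discussion of subsequent treatment at the final visit, which for Part 1 is when the primary sample is drawn. Part 2, by contrast, allows such treatment while follow-up continues (Protocol 5.2 and 7.8), so a rule there was unavoidable. The per-protocol set drops children who took prohibited medicine, the validity review can prompt a SAP amendment, and concomitant medication is tabulated by regimen.

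Much of this stands. A reader might infer that the SAP deliberately credits other drugs in Part 1 and rejects them in Part 2; the text supports only that Part 1 is silent. A reader might also infer that children positive at Day 30 are credited; if correctly dosed, they are discontinued and would normally be scored no cure. Retreatment after a positive Visit 8 or 9 with retention to Day 420 is an inference from the visit schedule, not a described pathway. Children who stop study drug early are a weak route, since they are asked to return only "to the investigational site for study assessments at Visits 3, 6, and 8 (EOT").

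What does not stand is that existing text closes the gap. The prohibited-medicine exclusion reaches only the per-protocol set, and Protocol 8.1 names only alcohol as prohibited. The validity review fixes no score, and a medication table does not change the endpoint.

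**Conclusion.** The point holds as a missing rule of minor weight. The absence of the rule is certain on the text; the number of children it touches is unknown. It is probably small: Protocol section 3 says that for infection of under one year "the percentage of patients cured (i.e., elimination of parasites) approaches 100"%, and Protocol 5.1 reports PCR turning negative within 60 days of treatment.

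A reader might infer that the primary superiority claim is in doubt. It is not: 67 reclassifications would be needed at the planned rate. The exposure is limited to the 60-day estimate (0.1 to 2.5 points under the assumed range), the exploratory 45% criterion (six cases at 110/200, so a reversal is unlikely unless the result is close to 105/200) and, slightly, the regimen difference. These sizes rest on 200 and 100 children, a 55% cure rate, and the assumed stratum sizes and retreatment shares.

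**What to change.** - Report, by regimen, the number of children given any antitrypanosomal drug other than assigned study drug between first dose and the 12-month sample.
- Add to the sensitivity analyses in SAP 6.2.1.1 a scoring of these children as no cure, in both regimens, for the primary variable and the 45% criterion. For 60 versus 30 days, show it beside the as-observed scoring.
- State in SAP 5.1 that prohibited medicine includes these drugs. This does not replace the rescoring, because the per-protocol set removes such children from the denominator instead of counting them as failures.
- Make this scoring the primary definition only if Part 1 is neither locked nor unblinded. SAP 3.2 already refers to subjects who have completed Part 1, and the documents do not show its lock status. After lock, redefinition would be a post-hoc endpoint change, so a supplementary table is the proportionate form.

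The cost is one flag from concomitant-medication data already collected under Protocol 8.1, one extra table and a possibly slightly lower cure rate. The change concerns scoring only and does not limit when a child may be treated.
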